signal of the intestinal wall, resulting in falsely high MSOT signals in the determination of inflammatory activity. Therefore, in this study, influences of a standardized dietary¹⁰ on the MSOT signal of the intestinal wall will be investigated in a longitudinal design and optoacoustic signals will be compared between subjects in fasting and postprandial states. Because the postprandial increase in intestinal blood flow is predominantly a result of the local presence of chyme in the intestine,¹¹ a simultaneous determination of intestinal transit of chyme during MSOT measurement would be helpful to validate whether postprandial changes in MSOT signals are attributable to hyperemia in the corresponding bowel segment. With MSOT, in addition to the determination of hemoglobin, the detection of exogenous chromophores is also possible. Therefore, in this study, oral administration of the nonabsorbable dye ICG will be used for noninvasive identification of the chyme.¹² We believe that the combination of exogenous and endogenous chromophores thus allows accurate co-localization and registration of intestinal wall blood flow patterns and chyme transit. This information enables accurate anatomical mapping of interfering influences on the determination of hemoglobin using MSOT.

The time course of postprandial hyperemia in the different sections of the gastrointestinal tract has been scientifically investigated in many studies. While an increase in blood flow in the stomach and duodenum can be detected after 30-60 minutes, it takes much longer for postprandial hyperemia to be detected in the areas used to measure inflammatory activity with MSOT in IBD such as the terminal ileum and sigmoid colon. An increase in blood flow in the ileum can be measured after 120 minutes at the earliest,¹ and the arrival of chyme in the colon and the accompanying local increase in blood flow occur after approximately 240-300 minutes.^{13,14} Therefore in this study postprandial changes in the MSOT hemoglobin signal will be investigated over period of 7 hours.

Bibliography

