- The quantitative amount of oxygenated/deoxygenated hemoglobin in the intestinal wall determined by MSOT differs between fasting persons and persons after ingestion food.
- The quantitative amount of oxygenated/deoxygenated hemoglobin in the intestinal wall determined by MSOT changes after the ingestion of food.
- The postprandial changes in the quantitative amount of oxygenated/deoxygenated hemoglobin in the intestinal wall determined by MSOT occur successively in subsequent sections of the gastrointestinal tract, from oral to aboral.
- A relationship exists between postprandial changes in the quantitative amount of oxygenated/deoxygenated hemoglobin in the wall of the gastrointestinal tract determined by MSOT and postprandial changes in Doppler sonographic signals in the major splanchnic arteries (truncus coeliacus, superior mesenteric artery, inferior mesenteric artery).
- The postprandial changes in the quantitative amount of oxygenated/deoxygenated hemoglobin in the intestinal wall determined by MSOT are associated with the presence of chyme in the lumen of the gastrointestinal tract.
- Measurement of ICG signals within the lumen of the gastrointestinal tract using MSOT after ingestion of ICG-containing food indicates the presence of chyme within the lumen of the gastrointestinal tract.
- A relationship exists between postprandial changes in the quantitative amount of oxygenated/deoxygenated hemoglobin in the wall of the gastrointestinal tract determined by MSOT and postprandial changes in the ICG signal determined by MSOT within the lumen of the gastrointestinal tract after ingestion of ICG-containing food.

Primary objectives:

- Comparison of oxygenated/deoxygenated hemoglobin signal in the wall of the gastrointestinal tract measured by MSOT between fasting subjects and subjects after ingestion of food.

Secondary objectives:

- Measurement of the postprandial change in the oxygenated/deoxygenated hemoglobin signal in the wall of the gastrointestinal tract measured by MSOT over time and over the different sections of the gastrointestinal tract.
- Comparison of the Doppler sonographic signal in the large arteries of the splanchnic area between fasting subjects and subjects after ingestion of food.
- Measurement of the postprandial change in the Doppler sonographic signal in the large splanchnic arteries over time and over the different splanchnic arteries.

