- Correlation between postprandial changes in the oxygenated/deoxygenated hemoglobin signal in the wall of the gastrointestinal tract measured by MSOT and postprandial changes in Doppler sonographic signals in the large arteries of the splanchnic artery.
- Comparison of the ICG signal in the lumen of the gastrointestinal tract measured by MSOT between fasting subjects, subjects after ingestion of food and subjects after ingestion of food containing ICG.
- Measurement of the postprandial change in the ICG signal in the lumen of the gastrointestinal tract measured by MSOT over time and over the different sections of the gastrointestinal tract in subjects after ingestion of food containing ICG.
- Correlation between postprandial changes in the oxygenated/deoxygenated hemoglobin signal in the wall of the gastrointestinal tract measured by MSOT and postprandial changes in the ICG signal in the lumen of the gastrointestinal tract measured by MSOT in subjects after ingestion ICG-containing food.

Study type

Since no data exist to support the hypothesis of this study to date, it is an exploratory study.

6. Target parameters

Study related measures and target
All MSOT measurements are taken over the gastric antrum, terminal ileum, transverse colon, and sigmoid colon.
Primary targets (obligatory):
Quantitative de-/oxygenated hemoglobin signal (in arbitrary units)
These target values are collected non-invasively using MSOT.
Secondary targets:
Qualitative and quantitative ICG signal (in arbitrary units)
Quantitative single wavelengths signal (in arbitrary units)
Optoacoustic spectrum (in arbitrary units, normalized)
These target values are collected non-invasively using MSOT.
Secondary targets (optional):
Doppler sonographic signals of the coeliac trunk, superior mesenteric artery, inferior mesenteric artery:

• Doppler sonographic spectrum• Doppler sonographic curve• Velocity profile• Flow profile• Flow volume• Resistance index• Pulsatility index
These target values are collected non-invasively using sonography.

7. Study design

Monocentric / multicentric

It is a monocentric diagnostic study with prospective data collection (Investigator Initiated Trial, IIT).

Study arms:

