A comparison is made between 3 study arms: A: Fasting, B: Standardised breakfast, C: Standardised breakfast with added ICG (250mg in 50ml aqua). As part of the crossover design, each subject will pass through all three study arms on three different days. There is a period of at least 48 hours between two consecutive study days for each subject.

Randomisation

Randomisation is not planned. As part of the crossover design, each subject passes through all three study arms. The order of the study arms is identical for each subject:

1. Study arm A: Fasting
2. Study arm B: Standardised breakfast
3. Study arm C: Standardised breakfast with added ICG

Blinding

No blinding is planned.

8. Study population

Inclusion and exclusion criteria

Inclusion criteria:

- Age over 18 years
- Written declaration of consent

Exclusion criteria

Generally valid:

- Pregnancy
- Nursing mothers
- Tattoo in the field of investigation
- Subcutaneous fat tissue over 3 cm
- Chronic or acute diseases of the gastrointestinal tract or symptoms suggestive of such a disease
- Diseases requiring acute treatment
- Lack of written consent

ICG related:

- Known hypersensitivity to ICG, sodium iodide or iodine
- Hyperthyroidism, focal or diffuse thyroid autonomy
- Treatment with radioactive iodine for the diagnostic examination of thyroid function within two weeks before or after the study
- Restricted renal function
- Intake of the following drugs: Beta-blockers, anticonvulsants, cyclopropane, bisulphite compounds, haloperidol, heroin, meperidine, metamizole, methadone, morphine, nitrofurantoin, opium alkaloids, phenobarbital, phenylbutazone, probenecid, rifamycin, any injection containing sodium bisulphite.

Subject number

As this is a pilot study, it is not possible to calculate the exact number of cases. It is planned to examine a total of 10 study subjects.

Recruitment measures

Volunteers will be informed by means of a public notice and via the homepage of the University Hospital Erlangen. If volunteers are willing to participate, they will be fully informed about the aims and methods (especially about the scientific/explorative nature of the study), the benefits and risks and the revocability of participation in the study. Each participant receives an expense allowance of 150€.

9. Study course

Procedure for informing about and obtaining consent

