The study starts for the participants at 10 pm on the day before the first examination day with adherence to the fasting period. On the first examination day, the preprandial measurement is performed at 8 am after 10 hours of fasting in all study arms. The preprandial measurement starts with the sonographic localisation of the sections of the gastrointestinal tract that will be examined in the following measurements with MSOT and Doppler sonography. Skin markings are made with a skin-compatible marker pen for better reproducibility of the following measurements. The further procedure of the preprandial measurement and each of the following postprandial measurements will follow an identical measurement protocol. A period of 20 minutes is planned for each measurement protocol. Depending on the study arm, the subjects remain fasting throughout all the measurements of the day (study arm A) or receive a standardised breakfast with or without ICG supplement (study arm B/C) 30 minutes after the start of the preprandial measurement. After the subjects have eaten the breakfast within 15 minutes, the first postprandial measurement takes place exactly 60 minutes after the preprandial measurement in all study arms. In the following 6 hours, further postprandial measurements are taken at 60-minute intervals, so that the last measurement takes place exactly 7 hours after the start of the preprandial measurement. 4 hours after breakfast, the subjects from study arms B and C receive another standardised meal to simulate regular food intake. This meal does not contain ICG. The subjects in study arm A remain fasting throughout all the measurements of the day.

On each measurement day two subjects are examined in parallel with a time offset of 30 minutes. This means that the entire examination for the second participant begins at 8:30 am.

[figure not shown]

Figure 1: Course of one examination day for one participant. X-axis is time in minutes with 0 being the beginning of the preprandial measurement at 8:00 or 8:30 am..

In a crossover design, each participant is examined on three measurement days according to the three study arms. There must be a minimum time interval of 48 hours between each examination day for the participant. The order of the examination days is predetermined:

1st examination day (study arm A): Fasting

2nd examination day (study arm B): Standardised breakfast

3rd examination day (study arm C): Standardised breakfast with ICG

[figure not shown]

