In addition, the study will be terminated for the individual participant if, as a result of adherence to the fasting period before the measurements and during the measurements in study arm A, complaints such as malaise, weakness, a strong feeling of hunger, stomach complaints, abdominal cramps or similar occur.

Termination criteria for the whole study:

A termination of the entire study is not planned

Statement on medical justifiability

Based on previous experience, the risk of undesired events associated with is considered extremely low.

No serious event has been reported so far, neither at our own site nor in literature. The majority of the reported (foreseeable) problems related either to the use of ultrasound gel for examination or the need to wear eye protection. The use of filter glass also explains the reported red-sightedness. This phenomenon was reversible within seconds. Table 1 shows the reported events from our study (MSOT_DMD, 67_18 B, Clinicaltrials.gov Identifier: NCT03490214).

	Muscular dystrophy Duchenne N=10	Healthy volunteer N=10
Reversible adverse events- no.		
Pressure of safety goggles	2 (20%)	
Coolness of Ultrasound-gel		4 (40%)
Red cast view		1 (10%)
Serious adverse events- no.	0 (0%)	0 (0%)

Table 1 – Reported events MSOT_DMD, 67_18 B

The occurrence of adverse side effects from the systemic use of ICG (Verdye, Diagnostic Green 5mg/ml) is very rare (<1 in 10 000). According to the manufacturer, the dye is not absorbed after oral application of ICG and is not subject to enterohepatic circulation. Therefore, the occurrence of systemic side effects from oral intake of ICG is very unlikely.

10. Biometrics

Explorative study: explanation of the statistical methodology, justification of the selected number of cases

Case number calculation:

As this is a pilot study and no information on the expected differences between the different groups is available yet, no case number calculation was performed. The number of cases given represents an estimate or is within the appropriate range for a pilot study.

Statistical methods:

The data is given as mean value with standard deviation. Correlations are given with the non-parametric Spearman correlation coefficient (R_s). According to the distribution on groups the differences of the mean values are examined statically with a nonparametric T-test (Mann-Whitney test) or ANOV. In all analyses an error level of <0.05 is considered statistically significant.

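### With a fixed A-B-C order, the primary fed-versus-fasting contrast is not tied to the same-day preprandial scan and is not analysed within subject

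*Combined protocol and SAP*

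**What the plan says.** All references are to the combined protocol and SAP.

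- **Order.** Section 7 (Randomisation) rules out randomisation and states: "The order of the study arms is identical for each subject". Section 9 (Time schedule) repeats it: "The order of the examination days is predetermined".
- **Primary objective (section 5).** "Comparison of oxygenated/deoxygenated hemoglobin signal in the wall of the gastrointestinal tract measured by MSOT between fasting subjects and subjects after ingestion of food". Section 6 makes the haemoglobin signal, in arbitrary units, the primary target. Section 7 (Study arms) describes the comparison as one between the three arms.
- **Same-day reference.** Section 9 (Time schedule): "the preprandial measurement is performed at 8 am after 10 hours of fasting in all study arms". No section says how this value enters the primary comparison.
- **Analysis (section 10, Statistical methods).** "the differences of the mean values are examined statically with a nonparametric T-test (Mann-Whitney test) or ANOV". No subject, baseline or period term is mentioned.
- **Wording that points the other way.** Section 4 describes a longitudinal design in which "optoacoustic signals will be compared between subjects in fasting and postprandial states". Section 5 also lists change after food as a hypothesis of its own, and postprandial change over time as a secondary objective.

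**The concern.** With one sequence for everyone, a difference between arms A and B is also a difference between day 1 and day 2. If post-meal values are compared directly across arms, a systematic change between days would be read as a food effect, or could hide one. The study exists to learn whether eating raises the MSOT signal enough to mislead the assessment of inflammation, so an estimate that mixes food with day weakens its main output. Random relocalisation error between days would add noise only.

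The named test raises a different problem. Mann-Whitney treats the same 10 people as two independent groups and discards the within-subject information that the crossover was set up to provide.

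**Working it through.** **Inputs.** n = 10 (section 8, Subject number). Error level 0.05 (section 10); two-sided is assumed because sidedness is not stated. The plan gives no effect size, SD, correlation or sample-size calculation, so there is no figure of its own to reproduce. Everything below that depends on a shift s, a same-subject correlation ICC between A_t and B_t, or a correlation r is an assumption shown over a range. The unit is the SD of B_t − A_t, for one bowel section, one haemoglobin species and one time point.

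**Step 1: bias.** Let d be the food effect and s an additive day 2 minus day 1 shift.

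- Raw contrast: E(B_t − A_t) = d + s, whether or not the test is paired. Pairing changes the variance, not the expectation.
- Change contrast: if a fraction q of s is already present at the preprandial scan, E[(B_t − B_0) − (A_t − A_0)] = d + (1 − q)s. This equals d only when q = 1.

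**Step 2: the named test.** The true variance of a paired difference is 2σ²(1 − ICC), whereas an unpaired test works with 2σ². The ratio is 0.7, 0.5 and 0.3 at ICC 0.3, 0.5 and 0.7. Rejection rates on raw values (exact Mann-Whitney, 40,000 simulations; paired t from the noncentral t with 9 df):

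| d + s (SD) | Mann-Whitney, ICC 0.3 | ICC 0.5 | ICC 0.7 | Paired t |
|---|---|---|---|---|
| 0 | 2.0% | 0.9% | 0.2% | 5% |
| 0.25 | 5.4% | 2.6% | 0.8% | 10.9% |
| 0.5 | 17.7% | 10.3% | 3.6% | 29.3% |
| 1.0 | 67.9% | 52.7% | 28.3% | 80.3% |

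A one-way ANOVA of A and B behaves much like Mann-Whitney: 2.3%, 1.0% and 0.2% at zero, and 73.7%, 58.9% and 31.9% at 1 SD.

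The table can be read in two ways. With s = 0 the rows below the first are power, and the unpaired test reaches 28-68% where a paired t reaches 80%. With d = 0 they are false positives caused by a day shift. The raw contrast cannot tell the two cases apart. Pairing alone makes a day shift more likely to reach significance (80% against 28-68% at 1 SD).

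**Step 3: what the same-day reference buys and costs.** Let r be the correlation between B_t − A_t and B_0 − A_0. The change contrast has variance 2(1 − r) on this scale. Its power for a 1 SD effect uses noncentrality √10 / √(2(1 − r)) with 9 df.

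| r | 0 | 0.3 | 0.5 | 0.7 | 0.8 |
|---|---|---|---|---|---|
| Variance relative to raw paired difference | 2.0 | 1.4 | 1.0 | 0.6 | 0.4 |
| Power, 1 SD effect (raw paired: 80%) | 51% | 66% | 80% | 95% | 99% |
| False positives, 1 SD shift, half present at the preprandial scan | 17% | 22% | 29% | 45% | 61% |

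If the whole shift is present at the preprandial scan, simulated false positives are 4.7-5.1% (paired t or signed-rank).

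Note that r is not the within-day correlation w of pre- and post-meal values. Under a simple equal-variance model, r = (w − ICC)/(1 − ICC). So w = 0.5 with ICC = 0.5 gives r = 0, and w = 0.8 with ICC = 0.5 gives r = 0.3/0.5 = 0.6. A low r is therefore plausible.

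**The case against.** **Fasting may mean the same-day state before the meal.** Section 4 and the change hypothesis in section 5 allow this, and arm order would then not affect a purely within-day contrast. A reader might infer that the plan explicitly puts the primary contrast on raw values; it does not. But section 7 sets the comparison between arms, and section 5 lists change separately from the primary objective, so the between-arm reading is the more natural one. What stands is that the contrast is not defined.

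**No day shift is shown.** This is correct. A reader might infer that the results will be biased. The documents give no evidence of a shift, and the common fast, identical measurement protocol and skin marking reduce variation between scans, though they do not exclude a shift. With the named tests, a 0.25 SD shift leaves false positives at 0.8-6.3%.

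**ANOVA could be run as repeated measures.** It could, but this is not stated. A subject term would mend the test size and precision, yet it cannot separate arm from day when everyone follows one sequence.

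**The study is an exploratory pilot.** This lowers the weight of a false significance claim. It does not help with a biased estimate that is carried into later work.

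**The change score may lose precision.** This stands, and it is why the raw paired difference should be reported beside it.

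**Conclusion.** The point holds as two distinct defects. (a) Arm and day coincide, and the same-day value that could largely separate them has no stated role, so a shift of s biases a raw between-arm estimate by exactly s. This is algebra for an additive shift; whether s differs from zero is unknown. (b) The unpaired test is wrong for crossover data whatever s is: it is conservative (about 0.2-2% instead of 5% at ICC 0.7 to 0.3) and loses power.

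Two stronger conclusions are tempting and not supported. One is that pairing would cure the bias; it corrects size and precision only. The other is that the fixed order must be changed; the data already planned allow a workable correction, with the limits in step 3. This should be changed before analysis. The main harm is an estimate that cannot be cleanly attributed to food, together with an inefficient test.

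**What to change.** 1. For the primary contrast, replace Mann-Whitney or the unspecified ANOVA with a within-subject analysis of (B_t − B_0) − (A_t − A_0): paired t, Wilcoxon signed-rank, or a mixed model with a subject effect.
2. State whether arm C, which also eats, counts as fed in the primary contrast.
3. Report the raw paired difference B_t − A_t and the preprandial values by day alongside it, so that a day shift is visible.
4. State as a limitation that arm contrasts, including those with C, remain confounded with day beyond what the preprandial value removes.

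This presumes that one primary section, haemoglobin species and time has been named from 4 × 2 × 7 = 56 candidates, which is a separate point.

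**Cost.** Items 1 to 4 change wording only; the scans are already planned. The downside is precision: the variance is 2(1 − r) times that of the raw paired difference, so the change score is worse when r is below 0.5. It also removes only an additive shift already present at the preprandial scan; a change in gain would need a ratio or log scale.

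**Optional stronger remedy, if the schedule allows.** Alternate A and B, keep C last, and fit a period term. This also covers additive day effects that arise after the preprandial scan, assuming no carry-over from B to A across the gap of at least 48 hours. Power for a 1 SD effect falls from 80.3% to 79.1% with a 5/5 split (variance factor (1/5 + 1/5)/4 = 0.100, 8 df), or to 77.4% with 6/4 ((1/6 + 1/4)/4 = 0.104).

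It needs an amendment and an allocation list. Section 9 says "On each measurement day two subjects are examined in parallel with a time offset of 30 minutes", so a 5/5 split needs at least one pair in different arms on the same day. That would place a fasting subject beside a fed one, and section 9 (Termination criteria) lists strong hunger in arm A among the reasons for ending participation. This practical cost should be weighed first.

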The regional blood flow in the intestinal wall and the distribution of gastrointestinal blood flow are also subject to strong postprandial changes. During absorption of food components, blood flow increases sequentially in the respective sections of the gastrointestinal tract, leading to postprandial hyperemia. Because postprandial hyperemia is particularly regulated locally by the presence of dietary components, there is a relationship between the sequential increase in blood flow in the intestinal wall and the peristaltic transport of chyme through the gastrointestinal tract. Postprandial hyperemia could also lead to an increase in the optoacoustic hemoglobin signal of the intestinal wall and thus have an impact on the assessment of inflammatory activity in IBD using MSOT. Additionally MSOT allows the identification of non-absorbable exogenous chromophores, such as indocyanine green (ICG), which could allow co-localization of the chyme in the intestinal lumen after oral application of ICG.

The purpose of this pilot study is to investigate in healthy volunteers whether, postprandial blood flow changes can be quantitatively measured using MSOT and whether these changes occur simultaneously with the gastrointestinal passage of the chyme as measured by the ICG signal in the intestinal lumen.

3. Responsibilities

Principle investigator

Dr. med. [name]

Department of Paediatrics and Adolescent Medicine

University Hospital Erlangen

[name]

[name]

[contact]

E-Mail: [contact]

Further investigators

Dr. med. [name]

Department of Paediatrics and Adolescent Medicine

University Hospital Erlangen

[name]

[name]

[contact]

E-Mail: [contact]

[name]

Department of Paediatrics and Adolescent Medicine

University Hospital Erlangen

[name]

[name]

E-Mail: [contact]

[name]

Department of Paediatrics and Adolescent Medicine

University Hospital Erlangen

[name]

[name]

Email: [contact]

Sponsoring

IZKF junior project (J89). Until the start of the project additional internal funds of the Department of Pediatrics and Adolescent Medicine, University Hospital Erlangen.

4. Scientific Background and derivation of the question

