- Active diagnostic device
- non-invasive
- Temporary use (<60 min)

There is a CE certification for this medical device (type designation according to imprint: Acuity Echo). A extension of the certification or conformity assessment procedure is not planned in this study. It is therefore a purely scientific pilot study. There is no dependency on the manufacturer, all diagnostic and analytical procedures are available to the study directors on site. No data is passed on to the manufacturer.

According to the Medical Device Regulation (MDR) 2017/745 and the Medizinproduktrecht-Durchführungsgesetz (MPDG), this study does not apply as “sonstige klinische Prüfung nach Art. 1 Medizinproduktedurchführungsgesetz: §3 Abs. 4”. The medical device is used within the scope of its intended purpose, without harmful or invasive measures (omission of Art. 62 MDR).

Adherence to energy levels

The laser safety and maximum permitted radiation dose for irradiation with laser pulses is regulated in the laser standards ANSI and IEC 60825. The MSOT system meets these standards and therefore remains below the MPE (maximum permissible exposure) limits for skin irradiation and is therefore considered safe.

Temperature increases due to MSOT in tissue

Optoacoustic imaging does not result in any significant temperature increase in the tissue. The absorption of a laser pulse in the tissue results in a local transient temperature increase of a few millikelvin. Depending on the duration of the examination and the skin type of the participant, temperature increases occur typically in the range of less than one degree Kelvin.

Histological changes in tissue

Histological changes in the target tissue and surrounding structures are neither expected nor have they been observed in previous preclinical and clinical studies.

Slight, reversible redness or warming might occur in very sensitive skin.

Such side effects are to be noticed at any time by the study participant or the examining doctor; the examination can then be interrupted or aborted. In any case, no irreversible damage is to be expected.

In general, the near infrared light used in MSOT can lead to retinal damage if the eye is irradiated. In order to prevent this, participants and examiners will wear appropriate laser safety glasses during the examination.

Since the data obtained is not used to interpret diagnostic results, there is no risk of possible misdiagnosis or incorrect display of data in this exploratory pilot study.

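### The plan rules out all blinding and makes no exception for image quantification, so knowledge of arm and time point could bias the fed-versus-fasting haemoglobin comparison; coding stored scans would be a cheap safeguard.

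*Combined protocol and SAP*

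**What the plan says.** Section 7 (Blinding) consists of one sentence: "No blinding is planned". It does not distinguish volunteers, operators and image readers.

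The primary objective in section 5 is "Comparison of oxygenated/deoxygenated hemoglobin signal in the wall of the gastrointestinal tract measured by MSOT between fasting subjects and subjects after ingestion of food". Section 6 gives the primary target as "Quantitative de-/oxygenated hemoglobin signal (in arbitrary units"), measured over four sites. The ICG signal, a secondary target, is taken from the lumen.

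An expected direction appears in the introductory summary before section 3: "Postprandial hyperemia could also lead to an increase in the optoacoustic hemoglobin signal of the intestinal wall". Section 4 adds approximate times at which blood flow should rise in the ileum and the colon.

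The stated safeguards concern acquisition. Section 9 (Time schedule) says "Skin markings are made with a skin-compatible marker pen for better reproducibility of the following measurements", and every measurement follows the same protocol. The available text contains no rule for placing a region of interest, no automated quantification, no coding of scans, no second reader and no check of reader agreement.

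**The concern.** Blinding can be applied at several points. It is impossible for the person who eats or fasts, and impractical for the operator. It is usually possible for whoever turns a stored image into a number, and the plan gives that up along with the rest.

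The endpoint makes this matter. A wall signal and a lumen signal have to be told apart in each image. If a person does that, small choices about where the wall begins and ends affect the haemoglobin value. A reader who knows the arm and the time also knows, from the plan's own background, which scans might be expected to rise. An arm-dependent shift in those choices would be systematic: averaging over volunteers does not remove it, and in the fed-minus-fasting difference it looks like postprandial hyperaemia. At stake is whether a reported food effect on the MSOT signal can be attributed to blood flow.

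**Working it through.** The plan has no figure of its own to reproduce: section 10 makes no sample-size calculation and gives no SD, effect size or reader variability. The check therefore has two parts: what could be coded, and what an assumed shift would do.

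**1. What could be coded**

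Inputs: 10 volunteers (section 8), 3 days (section 7), 4 MSOT sites (section 6), and 8 measurements per day, namely one preprandial and seven hourly ones up to 7 hours (section 9). I assume one stored scan per site and time.

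- All arms: 10 × 3 × 8 × 4 = 960 scans.
- Arms A and B only: 10 × 2 × 8 × 4 = 640 scans. Of these, 10 × 2 × 1 × 4 = 80 are preprandial, when both arms are fasting, so 560 are taken after the arms diverge.

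These counts describe the workload. They do not enter the error-rate calculation.

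**2. Illustrative effect on the false-positive rate**

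Suppose food has no true effect and reading adds a shift of *d* SDs of the within-subject fed-minus-fasting difference. The values *d* = 0.2, 0.3 and 0.5 are assumptions. The level is 0.05 (section 10), taken as two-sided because sidedness is not stated.

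*Paired t-test, n = 10.* The rejection probability is P(|T| > 2.262), where T is noncentral t with 9 df and noncentrality d√10.

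| d | d√10 | False-positive rate |
|---|---|---|
| 0 | 0 | 5% |
| 0.2 | 0.632 | 8.8% |
| 0.3 | 0.949 | 13.6% |
| 0.5 | 1.581 | 29.3% |

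*Mann-Whitney, 10 versus 10.* Section 10 names Mann-Whitney or ANOVA, not a paired t-test. Mann-Whitney ignores the pairing, so the result depends on the correlation ρ between a volunteer's two days, which the documents do not give. With a signal SD of 1, the SD of the difference is √(2(1 − ρ)), so the shift in signal SDs is d√(2(1 − ρ)). At ρ = 0.3 and d = 0.5 this is 0.5 × √1.4 = 0.592. Simulation with normal data (100,000 runs per cell, exact critical value) gives:

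| ρ (assumed) | d = 0 | d = 0.2 | d = 0.3 | d = 0.5 |
|---|---|---|---|---|
| 0 | 4% | 8% | 13% | 28% |
| 0.3 | 2% | 4% | 7% | 18% |
| 0.5 | 1% | 2% | 4% | 10% |
| 0.7 | 0.2% | 0.5% | 1% | 4% |

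The paired-t figures are thus close to the top of the range. With positive correlation the unpaired test is conservative, and part of the inflation is absorbed: at ρ = 0.5 the rate stays below 5% for d = 0.2 and 0.3. The rate still rises with the shift in every row. Whatever the test, the estimated difference itself is displaced by the full shift.

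**The case against.** The strongest objection is that the reading step is not described at all. Manual selection of the wall is deduced from the words wall and lumen. If quantification is automated, reader bias would be small. Some pages are missing from the text available for review, so a reading procedure there cannot be excluded. This stands, and it is why the point is conditional. It does not remove the need to change a sentence that excludes blinding without qualification.

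The study is also a declared exploratory pilot. That lowers the severity, although section 10 still applies a 0.05 threshold.

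Five stronger readings are tempting, and the documents do not support them:

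- *The unblinded study team does the reading.* Section 9 (Study-related risks of MSOT) says only that "all diagnostic and analytical procedures are available to the study directors on site", in a statement about independence from the manufacturer. It names no reader and does not say what a reader would know.
- *The fixed order makes reader bias worse because nothing offsets it.* Section 7 does say "The order of the study arms is identical for each subject", but a randomised order would not offset bias in a reader who knows the arm. Fixed order matters here only because the examination day reveals the arm, so the day must be hidden too.
- *The bias could never be undone.* If scans are stored, they can be re-read masked later.
- *The bias must run upwards.* The hypotheses in section 5 are non-directional, and section 4 calls the effect unclear. The summary raises the possibility of an increase, which gives a reader an expectation but does not establish which result would be favoured.
- *The trial's error rate is 9% to 29%.* Those figures belong to a test that the plan does not name and to shifts with no source in the documents.

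One partial protection exists. Each day includes a fasting preprandial measurement, so analysing change from baseline would cancel a reading offset that is constant over the day. It would not cancel one that differs between time points, and section 10 does not specify such an analysis.

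**Conclusion.** The point holds in a limited form. The plan excludes blinding everywhere, and the available text offers no masked or automated quantification of a wall signal that is compared between states the reader could know. If a reader chooses the wall region, the primary comparison is open to expectation bias of unknown size.

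The illustration runs from 9%, 14% and 29% (paired t-test) to about 4%, 7% and 18% (Mann-Whitney at an assumed correlation of 0.3), and lower at higher correlation. It rests on assumed shifts of 0.2, 0.3 and 0.5 SD, normal data, two-sided testing and one test per comparison. It shows the possible scale of the problem and does not predict what will happen in this trial. Severity is modest; the case for acting is that the remedy is cheap.

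**What to change.** Replace the sentence in section 7 (Blinding) with:

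> Volunteers and operators are not blinded. Before quantification, stored MSOT scans are coded by a team member who does not read them, so that arm, day and time point are hidden. Scans may be grouped by volunteer under a code and are read in random order. Wall regions are drawn and haemoglobin values locked with the ICG channel hidden; lumen regions and the ICG signal are read in a separate later step with the ICG channel shown. The code is opened after all values are locked.

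Grouping by volunteer lets the reader match regions within a person. The separate second step keeps ICG available as the plan's own marker of chyme. Apply the same coding to Doppler recordings if they are stored. If quantification is in fact automated, describe the procedure instead.

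**Cost:** a renaming script, a short procedure and a key-holder from the existing team; no extra visit and no burden on volunteers. Reading must wait until scans are coded.

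**Limits:** masking is partial where gastric content is visible or where the reader also scanned the volunteer. Coding does not remove bias at acquisition, since the operator knows the condition, and it does not remove the confounding of arm with fixed order.
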